7. DATA COLLECTION

Assessment of Treatment Efficacy

Baseline and Treatment Efficacy Assessment Forms:

1. Demographics
2. Tinnitus Description and History Form
3. Global Bothersome Scale (GBS)
4. Tinnitus Functional Index (TFI)
5. Momentary Assessment of Tinnitus Questionnaire (MAT)
6. Patient Health Questionnaire (PHQ-9)
7. Patients' Global Impression of Change (PGIC)

The effects of the treatment will be assessed using repeat administration of GBS, TFI, MAT, PHQ-9, and PGIC.

Participants will be asked to complete forms 1-6 (detailed above) immediately before each of two sessions as **baseline assessment**, with Demographics and Tinnitus Description and History Form only required before the first session. One hour and then one day following each intervention, participants will complete EMA. One week following each session, participants will complete GBS, TFI, MAT, PHQ-9, and PGIC. These constitute the **treatment efficacy assessment**. In total, each participant will complete the baseline assessment at two timepoints and treatment efficacy assessment at 6 timepoints. The two sessions will be 14 days (2 weeks)

apart. These questionnaires can be completed online via a link provided through REDCap in an email to the participant. At 14 days after administration of nitrous oxide, we expect the effects of nitrous oxide to wear off fully and patients' tinnitus should have returned to baseline. The baseline assessment for the second session will take place no sooner than 14 days after the first session, and therefore will assess whether this washout period of 14 days is accurate. The patient will not be allowed to participate in the second arm of the study until their Global Bother Scale score is within one category of their baseline score.

Assessment of Treatment Safety

Treatment safety will be assessed at several levels: adverse events (AE) related to (i) cardiovascular status; (ii) respiratory function; (iii) central nervous system; (iv) psychiatric symptoms,.

- (i) Cardiovascular AEs, such as hyper- and hypotension, tachy-/bradycardia, will be identified by continuous hemodynamic monitoring during and after the treatment
- (ii) Respiratory AEs, such as respiratory depression and desaturation, will be identified by continuous pulse oximetry during and after treatment
- (iii) Central nervous system AEs will be assessed clinically.
- (iv) Psychiatric AEs, will be assessed clinically.

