9. DATA ANALYSIS

Standard descriptive statistics will describe the study population, responses to assessments, and severity of tinnitus. Data will be analyzed using SAS version 9.4 statistical software (SAS Institute, Inc. Cary, NC).

Aim 1. To evaluate the effect of nitrous oxide as treatment of tinnitus.

The primary efficacy parameter will be the in the change in TFI. Secondary outcome measure will be the change in MAT. **Baseline** TFI and MAT will be defined as those determined immediately before a session. **Post-treatment** TFI and MAT will be compared to **baseline** TFI and MAT at each time point. A mixed model analysis using SAS Proc Mixed procedure will be used to explore the change in TFI score after treatment as compared to after placebo through exploration of the interaction effect of time*treatment. The mixed procedure allows for exploring information from measures nested within subjects nested within treatment groups. In addition, this analytical approach allows for investigation of the carry-over effect due to cross-over design.

And finally, the number of subjects with 13 or more points difference in TFI (clinically important difference)[16] after each treatment arm will be identified and compared between active and placebo treatments using McNemars test.

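### The pre-session-2 assessment is meant to test the 14-day washout, but it is taken only once bother is within one category of baseline, which biases the check toward recovery when a persisting effect is large

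*Combined protocol and SAP*

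**What the plan says.** Section 7 (Data Collection) gives the washout expectation, "we expect the effects of nitrous oxide to wear off fully" by 14 days, and cites no data for it. It then gives the second baseline a purpose, as an assessment made "no sooner than 14 days after the first session, and therefore will assess whether this washout period of 14 days is accurate". The next sentence sets an entry rule, with the participant's baseline as the reference: "The patient will not be allowed to participate in the second arm of the study until their Global Bother Scale score is within one category". No time limit is given.

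The timing of the forms, which include GBS and TFI, is set in the same section: "Participants will be asked to complete forms 1-6 (detailed above) immediately before each of two sessions as" the baseline assessment. Section 9 (Data Analysis) uses the same anchor: baseline "TFI and MAT will be defined as those determined immediately before a session".

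Follow-up after each session ends at one week: "One week following each session, participants will complete GBS, TFI, MAT, PHQ-9, and PGIC". The schedule is summed up as "each participant will complete the baseline assessment at two timepoints and treatment efficacy assessment at 6 timepoints".

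The synopsis, Section 6 and one sentence of Section 7 give a fixed two-week interval between sessions. The minimum of 14 days and the open-ended bother rule in Section 7 imply a variable one.

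**The concern.** The washout check is conditioned on the recovery it is supposed to test. If a nitrous-first participant is more than one bother category better at day 14, session 2 is postponed. The baseline forms move with the session, so the score that enters the check is taken after more of the effect has faded. If bother never returns to within one category, there is no second baseline at all.

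This matters because the crossover rests on the 14-day washout, and the second baseline is the only empirical test of it that the plan describes. Section 9 says that the mixed model allows carry-over to be investigated, but gives no term, test or decision rule.

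A second, separate limitation is that day 14 is observed after session 1 only, although every participant receives both gases.

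**Working it through.** **1. The schedule.** Efficacy timepoints are 1 hour, 1 day and 1 week after each session: 3 × 2 = 6, which reproduces the plan's figure. With two baselines, no slot is left for day 14 after session 2.

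**2. Bias from the bother rule, in TFI points.** The documents give no SD, no link between bother categories and TFI, and no decay rate, so the inputs here are assumptions:
- Starting TFI uniform on 40 to 100, and bother categories 20 TFI points wide.
- Noise SD of 6 points in reading the category.
- 30% of nitrous-first participants have a residual improvement D at day 14, and the rest have none.
- The residual halves every 2 weeks, and the rule is re-checked weekly.

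The recorded residual is the one present when the participant first passes the rule. Hidden share = 1 − recorded mean / true mean.

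| D | True mean at day 14 | Hidden | Recorded mean |
|---|---|---|---|
| 13 | 0.30 × 13 = 3.9 | about 1% | 3.9 × 0.99 = 3.9 |
| 20 | 0.30 × 20 = 6.0 | about 5% | 6.0 × 0.95 = 5.7 |
| 25 | 0.30 × 25 = 7.5 | about 10% | 7.5 × 0.90 = 6.8 |
| 35 | 0.30 × 35 = 10.5 | about 26% | 10.5 × 0.74 = 7.8 |
| 45 | 13.4 (0.30 × 45 = 13.5, less a small floor effect at TFI 0) | about 41% | 13.4 × 0.59 = 7.9 |

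With a 1-week half-life, the hidden share at 35 points is 35%. In the last two rows the recorded mean hardly moves while the true residual rises from 10.5 to 13.4.

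**3. The same question in category units.** This uses a different set of assumptions: five categories with entry in the top three, individual effects with a CV of 50%, noise SD of 0.3 to 1.0 category, weekly re-checks and a 1-week half-life. The low end of each understatement range is small noise using only those who pass on day 14. The high end is large noise with postponed scores included.

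| Mean persisting effect (categories) | Understated by | Pass on day 14 after nitrous oxide |
|---|---|---|
| 0.25 | 1% to 38% | 87% to 100% |
| 0.5 | 4% to 44% | 82% to 98% |
| 1 | 20% to 55% | 67% to 79% |
| 2 | 48% to 71% | 35% to 38% |

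After placebo, 90% to 100% pass. The residual was understated in every scenario.

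**4. Precision, with no bias involved.** Section 5 gives at least 30 evaluable participants and Section 6 equal allocation by sequence, hence about 15 per sequence. Assume an SD of change of 15 TFI points. The 95% half-width for the day-14 difference between nitrous oxide and placebo is:
- session 1 only, between sequences: 1.96 × 15 × √(4/30) = 10.7 points;
- both sessions, within person, correlation 0: 1.96 × 15 × √(2/30) = 7.6 points;
- both sessions, within person, correlation 0.3: 1.96 × 15 × √(2 × 0.7/30) = 6.4 points.

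**The case against.** Several stronger readings are tempting, and the documents do not support them.

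- *A reader might infer that any persisting effect is understated.* The rule tolerates a full category of change, so smaller residuals mostly pass and are recorded. At 13 TFI points, the plan's own clinically important difference, about 1% is lost in the TFI model. Loss at small effects becomes material only if bother scores are noisy.
- *A reader might infer that the data will look as if washout succeeded.* In the TFI scenarios with a 2-week half-life, 59% to 99% of the residual stays visible. Postponements are themselves a signal: at 35 points about 20% of nitrous-first participants would fail the rule on day 14, or about 3 of 15.
- *A reader might infer that the missing day-14 form after session 2 adds to the bias.* It does not. Without the bother rule, nitrous-first against placebo-first at the second baseline would be a valid randomised comparison.
- *A reader might infer that the trial cannot describe duration of effect.* TFI is measured at 1 week after both sessions and at 14 days or later after session 1. Duration is not an aim of the study.

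Three further points stand in the plan's favour. The text does not say when the qualifying GBS is taken or that a failed day-14 set is discarded; if such scores were kept and used, the bias could be avoided. Section 3 puts the offset of the drug's effect within minutes, so a large residual at two weeks may be unlikely, although the primary outcome at 1 week presumes an effect that outlasts the gas. And with a half-width of 10.7 points, the gap between 10.5 and 7.8 would seldom change a formal conclusion in a trial of this size.

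The conditioning itself is not answered. Followed as written, the second baseline moves with the session, and nothing provides for a fixed day-14 score. The rule is also two-sided: it postpones participants who worsen as well as those who remain improved.

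**Conclusion.** The concern holds in a limited form. The second baseline cannot fairly assess a 14-day washout, because a participant outside the bother limit on day 14 has it measured later or not at all. The direction is toward a smaller apparent residual.

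The size depends on assumptions that the documents cannot settle: the width of a bother category in TFI points, the noise in bother scores, the share of persisters and the rate of decay. Under those used here, the hidden share is negligible below about one category (1% to 5% at 13 to 20 points) and material above it (10%, 26% and 41% at 25, 35 and 45 points). Noisier bother scores would widen it.

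The absence of a day-14 score after session 2 is a separate matter of precision: a half-width of about 10.7 points, against 6.4 to 7.6 if both sessions were covered, given an SD of change of 15 and a within-person correlation of 0.3 to 0.

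**What to change.** 1. Send the GBS and TFI REDCap link at a fixed day 14 after session 1 to every participant, whether or not session 2 goes ahead that day, and keep that score. When session 2 takes place on day 14, the pre-session forms serve as the day-14 score.
2. Replace the sentence giving the second baseline its purpose with a defined check: fixed day-14 TFI minus pre-session-1 TFI, nitrous-first against placebo-first. A postponed pre-session-2 score should not be substituted.
3. Report, by sequence, how many participants fail the bother rule on day 14, in which direction, and how long session 2 is delayed.
4. Optionally, send the same form at day 14 after session 2, so that a within-person comparison can be added. The session-1 comparison should remain the main washout check.
5. Leave the session-2 entry rule unchanged. Reconcile the fixed two-week interval in the synopsis, Section 6 and Section 7 with the 14-day minimum and open-ended rule in Section 7.

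The cost is one or two short online forms on a system already in use, about one more week of remote follow-up if the session-2 form is added, and some non-response. A day-14 score not collected during the trial cannot be recovered at analysis.

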6. METHODS

Study Design

This is a prospective, randomized, double-blinded, placebo-controlled crossover trial where 40 patients will undergo two treatment sessions in randomized order. In one session, subjects will receive up to 50% nitrous oxide/50% oxygen for 40 minutes ("Treatment"). In the other session, subjects will receive up to 50% nitrogen [inert]/50% oxygen for 40 minutes ("Placebo"). The two sessions will be held 2 weeks apart and will be indistinguishable from each other in setting, setup, and monitoring.

No pre-enrollment laboratory assessments will be required. However, a health history will be taken at screening.

Randomization

Each participant will be randomly assigned to either the “Treatment first” or “Placebo first” group. The randomization scheme will use permuted blocks of randomly varying sizes generated by the study statistician using SAS statistical software and a password-protected Microsoft Excel spreadsheet will be used to create and store the study IDs and the randomization order. Each block will contain equal numbers of assignments to the treatment first and placebo first in randomized order. To account for the anticipated 20% dropout rate (i.e., as a result of withdrawal, being lost to follow-up, and so on), the randomization table will be generated for 50 subjects.

Blinding

Participants will be blinded to the randomization order. Nitrous oxide is a colorless and odorless gas, which makes it unlikely for participants to identify the group assignment. Likewise, the study setup will be identical for both sessions, which will make an inadvertent unblinding of the study unlikely. For the anesthesiology team responsible for the administration of the nitrous oxide treatment, the group assignment will be known. This team is completely separate from the team assessing the study outcomes, which will be blinded to the treatment received. Treatment administration and outcomes assessment will also be physically separated in different rooms within the Clinical Research Unit (CRU) to prevent unblinding. To assess the integrity of the blind, subjects will be asked immediately after each administration to guess which treatment – active or placebo they just received.

Setting

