The study will be performed in the Clinical Research Unit (CRU) at the Center for Applied Research Sciences, located on the 4th and 5th floors of Barnard Hospital. The CRU is staffed by nurses, technicians, and medical assistants with experience in implementing clinical research studies, including specialized protocol-required procedures. The facility consists of 6 rooms and 12 semi-private beds, and is equipped with state-of-the art anesthesia machines, monitoring and anesthesia equipment, and resuscitation equipment and devices. The CRU has anesthesia equipment set up to allow for treatment of two participants at once. We will pay the CRU an annual fee of \$500 for this active protocol.

Administration of Study Treatment

Except for the choice of gas (nitrous oxide or nitrogen [inert]; both mixed with 50% oxygen), treatment sessions will be identical. The gas mix will be administered via a standard anesthesia face mask through tubing connected to the inhalation apparatus. Inhaled and exhaled gas concentrations of nitrous oxide, oxygen and nitrogen will be monitored and adjusted according to protocol. Total gas flow will be 2-4 L/min.

Participants will be NPO (although liquids may be freely consumed) for 2 hours prior to each intervention session as a precaution for possible nausea. Participants will be monitored during and after the treatment according to American Society of Anesthesiologists (ASA) standard, which includes continuous 3-lead ECG, pulse oximetry, non-invasive blood pressure and end tidal CO₂ under the supervision of an attending-level anesthesiologists.[15] After the 40 minute treatment session, participants will be monitored in the CRU for 1 hour. Participants will then be asked to complete the Momentary Assessment of Tinnitus (MAT) questionnaire before leaving. A study team physician will determine when the participant meets criteria for discharge as described by the ASA standard.

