10. RISK ASSESSMENT

Nitrous oxide. The side effects of nitrous oxide are well known to anesthesiologists. The dose (50%) and duration (40 minutes) used in this protocol are considered extremely safe and of low risk. Similar doses and durations are used in everyday dental practice without vital sign monitoring or supervision by a resuscitation-trained physician. With this dose of nitrous oxide, sedation may occur but not general anesthesia or respiratory depression. Previous evidence shows that the inactivating effect of nitrous oxide on vitamin B12 is dose and duration-dependent and are minor when used as described in this protocol. An increase in plasma homocysteine by +25% and return to baseline within the next 24 hours is expected. Minor side effects after nitrous oxide exposure such as nausea and vomiting may occur which are typically self-limited and short. As a precaution against nausea, patients will be NPO for 2 hours prior to each intervention session, although liquids may be freely consumed. If a patient develops moderate to severe nausea and vomiting, we will administer 4mg of ondansetron.

Questionnaires. Participants may experience frustration and/or boredom completing the questionnaires. The participants may refuse to answer any questions for any reason.

REFERENCES

2. Lechtenberg, Richard, and Abraham Shulman. "Benzodiazepines in the treatment of tinnitus." *The Journal of Laryngology & Otology* 98.S9 (1984): 271-276.
3. Lockwood, Alan H., Richard J. Salvi, and Robert F. Burkard. "Tinnitus." *New England Journal of Medicine* 347.12 (2002): 904-910.
4. Langguth, Berthold, Richard Salvi, and Ana Belén Elgoyhen. "Emerging pharmacotherapy of tinnitus." *Expert opinion on emerging drugs* 14.4 (2009): 687-702.
5. Langguth, Berthold, and Ana Belén Elgoyhen. "Current pharmacological treatments for tinnitus." *Expert opinion on pharmacotherapy* 13.17 (2012): 2495-2509.
6. Beebe Palumbo, Devon, et al. "The Management and Outcomes of Pharmacological Treatments for Tinnitus." *Current neuropharmacology* 13.5 (2015): 692-700.
7. Drug Therapies, American Tinnitus Association <https://www.ata.org/managing-your-tinnitus/treatment-options/drug-therapies>.

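### Section 7 identifies respiratory depression by pulse oximetry on 50% oxygen, where cases can be missed, and does not use the end-tidal CO2 already monitored

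*Combined protocol and SAP*

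**What the plan says.** Section 7 (Data Collection, Assessment of Treatment Safety, item ii) names two respiratory adverse events and one means of finding them: "Respiratory AEs, such as respiratory depression and desaturation, will be identified by continuous pulse oximetry during and after treatment". The neighbouring items for central nervous system and psychiatric events rely on clinical assessment; item (ii) does not mention it. The protocol gives no definition or limit for a respiratory event.

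Section 6 (Study Design) sets the active exposure: "subjects will receive up to 50% nitrous oxide/50% oxygen for 40 minutes". Under Administration of Study Treatment the two sessions differ only in the gas: "nitrous oxide or nitrogen [inert]; both mixed with 50% oxygen".

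The same part of Section 6 requires a wider set of signals than item (ii) uses. It says "Participants will be monitored during and after the treatment according to American Society of Anesthesiologists (ASA) standard", and lists "continuous 3-lead ECG, pulse oximetry, non-invasive blood pressure and end tidal CO₂", with an attending-level anesthesiologist supervising. It adds: "After the 40 minute treatment session, participants will be monitored in the CRU for 1 hour". The oxygen breathed in that hour is not stated.

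Section 10 gives the expectation: "With this dose of nitrous oxide, sedation may occur but not general anesthesia or respiratory depression".

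**The concern.** Respiratory depression and desaturation are different events, and item (ii) itself lists them separately. Oximetry measures oxygen saturation, not ventilation. When a person breathes enriched oxygen, ventilation can fall a long way before saturation moves. The method named for both events therefore suits one of them and, while the gas is running, is a poor detector of the other. End-tidal CO2, which follows ventilation directly, is monitored in the same sessions, but nothing in the protocol connects it to the identification of adverse events.

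What is at stake is how the respiratory safety result can be read. So far as cases are found through oximetry, the observed count reflects the true frequency multiplied by a low detection probability. A count of zero or near zero would then say little about whether the Section 10 expectation is right. Comparing the sessions does not repair this, because the oxygen fraction, and so the masking, is the same under nitrous oxide and placebo.

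**Working it through.** The plan states no figure on this point, so there is none to reproduce. The check is whether saturation on 50% oxygen responds to hypoventilation.

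**Inputs from the protocol.** Inspired oxygen fraction (FiO2) 0.50 in both sessions, for 40 minutes (Section 6).

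**Assumptions, not in the protocol.** Sea level (760 mmHg, less 47 mmHg water vapour, gives 713); respiratory quotient R from 0.8 to 1.0; alveolar-arterial gradient 10 to 100 mmHg on 50% oxygen and 5 to 15 mmHg on room air; steady state; no shift of the saturation curve. At steady state, doubling arterial CO2 pressure (PaCO2) from 40 to 80 mmHg corresponds to roughly halved alveolar ventilation.

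**Formulas.**
- Alveolar oxygen: PAO2 = FiO2 × 713 − PaCO2 × (FiO2 + (1 − FiO2)/R)
- Arterial oxygen: p = PAO2 − gradient
- Saturation (Severinghaus): S = 1 / (1 + 23400/(p³ + 150p))

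**Alveolar oxygen on 50% oxygen.**
- R = 0.8, PaCO2 40: 356.5 − 40 × 1.125 = 311.5 mmHg
- R = 0.8, PaCO2 80: 356.5 − 80 × 1.125 = 266.5 mmHg
- R = 1.0, PaCO2 40 and 80: 356.5 − 40 = 316.5 and 356.5 − 80 = 276.5 mmHg

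**Least favourable case at PaCO2 80** (R = 0.8, gradient 100): p = 166.5, so p³ + 150p ≈ 4,640,700; 23400/4,640,700 ≈ 0.0050; S ≈ 99.5%.

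**Saturation over the assumed ranges.**

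| Inspired oxygen | PaCO2 40 | PaCO2 80 | PaCO2 at which S reaches 94% |
|---|---|---|---|
| 50% (gradient 10-100) | 99.8-99.9% | 99.5-99.9% | about 165-276 mmHg |
| Room air (gradient 5-15) | 96.6-98.0% | 73.5-92.3% | about 54-74 mmHg |

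At PaCO2 100 mmHg on 50% oxygen, saturation is still 99.2-99.8%.

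**Sensitivity to mask leak.** Suppose leak lowers inspired oxygen to 35% (an assumed value), with R = 0.8 and PaCO2 80. Then PAO2 = 249.55 − 80 × 1.1625 = 156.55 mmHg, and saturation is 99.1% with a gradient of 20 or 97.5% with a gradient of 60. The direction does not change.

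**Reading.** On 50% oxygen, a doubling of PaCO2 moves saturation by a few tenths of a percentage point at most. The room-air row is only a comparison, but it shows that the enriched oxygen causes the insensitivity. The result applies while the gas is inhaled. It cannot be carried over to the following hour; if participants then breathe room air, oximetry is more informative.

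**The case against.** The strongest reply is that this is a gap in wording with little consequence. End-tidal CO2 is monitored during and after treatment under an attending-level anesthesiologist, who would see hypoventilation on the trace. Section 8 has the principal investigator and coordinator watch for adverse events throughout, and sends serious or unexpected events to the DSMC; neither route is restricted to what oximetry finds. Item (ii) does not say that other signals are excluded. The only stated aim is efficacy (Section 1), Section 9 plans no respiratory endpoint, and 40 participants could not estimate the rate of an uncommon event well under any wording. The physiological inputs are all external.

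Much of this stands. It rules out several stronger readings that a reader might infer:
- *That the trial would report no respiratory depression whether or not any occurred.* The supervising anesthesiologist and Section 8 mean that a case could still be reported.
- *That any case would have to count as unexpected, and so be lost to the DSMC.* Section 10 does not expect the event, but Section 7 names it as one to look for, so its classification is not settled.
- *That participants are unprotected.* The CO2 monitoring is already required.
- *That the CO2 data are already on file.* Section 6 says the signal is monitored; nothing says it is captured as study data.

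What the reply does not remove is that the written rule for identifying respiratory events points to a signal that is insensitive to one of the two events it names, and no text brings the CO2 signal into that rule. Other routes make under-counting less likely; they do not make ascertainment systematic.

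**Conclusion.** The concern holds as a defect of adverse event ascertainment. During gas delivery the only signal named in item (ii) is nearly unresponsive to hypoventilation, so respiratory depression can be under-counted in both sessions, and a low count would not by itself confirm the Section 10 statement. The masking rests on textbook physiology under the assumptions listed, not on figures from the protocol, but it persists across every range tried. How many cases would be missed cannot be calculated, because the protocol gives no event rate and no event definition. The efficacy analyses are untouched. Severity is minor to modest.

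**What to change.** Reconcile Sections 6 and 7. In item (ii), state that respiratory depression is identified from the end-tidal CO2 already monitored under Section 6, and desaturation from pulse oximetry. State that identified events are captured as study data, name where they are recorded (the protocol describes no form for this), and add to Section 9 a descriptive table of respiratory events by gas. The anesthesiology team should set the event limits; none is proposed here.

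The cost is a short text change and a small amount of added data capture. No new monitoring is needed. The drawback is that mask leak will produce some artefactual events.

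### Central nervous system and psychiatric adverse events have no scheduled enquiry after discharge, and the PHQ-9 has no stated safety review

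*Combined protocol and SAP*

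**What the plan says.** Section 7 (Assessment of Treatment Safety) names four domains. Cardiovascular events "will be identified by continuous hemodynamic monitoring during and after the treatment", and respiratory events are covered by continuous pulse oximetry over the same window. The other two get one line each: "Central nervous system AEs will be assessed clinically" and "Psychiatric AEs, will be assessed clinically". No timing, assessor, instrument or grading is given for either.

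Section 6 (Administration of Study Treatment) sets the observation period: "After the 40 minute treatment session, participants will be monitored in the CRU for 1 hour". It then says "A study team physician will determine when the participant meets criteria for discharge".

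Section 7 (Assessment of Treatment Efficacy) sets the later contacts: "One hour and then one day following each intervention, participants will complete EMA" (the abstract calls this questionnaire the MAT), and "One week following each session, participants will complete GBS, TFI, MAT, PHQ-9, and PGIC". On mode, "These questionnaires can be completed online via a link provided through REDCap in an email to the participant". The PHQ-9 is also completed before each session. It is listed only among the efficacy forms. The stated condition for entering session 2 concerns the Global Bother Scale.

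Section 8 has the principal investigator and coordinator watch for adverse events throughout and report them once they learn of them. A safety committee investigates serious or unexpected events. Section 2 states that patients with depression are eligible.

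**The concern.** Two of the four safety domains have neither a method nor a time at which anyone asks. Once a participant leaves the CRU, the plan looks for benefit at one day and one week but schedules no question about harm. A central nervous system or psychiatric event that begins after discharge may therefore be recognised late, or not be entered as an adverse event.

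The PHQ-9 raises a related issue. The trial collects mood scores from a group that includes people with depression. It states no threshold, reviewer, time to review or action if a score gets worse, and Section 9 plans no analysis of the PHQ-9 or of safety.

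What is at stake is participant care and a complete safety record. The TFI and MAT comparisons are not touched.

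**Working it through.** No power or sample-size figure bears on this, so the check is to lay out the described contacts and see where each kind of event would surface.

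| Time, for each session | What is described | Setting | Adverse-event question listed |
|---|---|---|---|
| Before gas | Baseline forms, including PHQ-9 | Online completion allowed; participant then attends | None |
| During gas | Standard anesthesia monitoring | CRU | Clinical assessment, timing not stated |
| 1 hour after | Monitoring, MAT, physician's discharge decision | CRU | Clinical assessment, timing not stated |
| 1 day after | EMA (MAT in the abstract) | Online completion allowed | None |
| 1 week after | GBS, TFI, MAT, PHQ-9, PGIC | Online completion allowed | None |

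**Plan's own count.** Section 7 gives 6 efficacy time points per participant. Three times (1 hour, 1 day, 1 week) × 2 sessions = 6, which agrees. The 1-hour forms are completed before leaving, so 2 × 2 = 4 of the 6 fall after discharge.

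**Observation time.** 40 + 60 = 100 minutes per session, unless the physician delays discharge. The first PHQ-9 after gas comes on day 7.

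**Participants given nitrous oxide in session 2.** Section 5 enrolls 40 to obtain at least 30 evaluable, and the blocks in Section 6 balance the two orders. With an even split, 40/2 = 20 if everyone completes and 30/2 = 15 if 30 do.

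**PHQ-9 forms.** Each completing participant gives 2 before sessions and 2 at one week, 4 in all. One of the one-week forms follows nitrous oxide, so there are 30 to 40 such forms with no described safety review.

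**Where events would surface.**
- Depressive worsening after session 1: in the one-week PHQ-9 and again in the PHQ-9 before session 2, at least 14 days after session 1. It is recorded as a score, with no step that handles it as an adverse event.
- Depressive worsening after session 2: in the one-week PHQ-9 only, which belongs to the last described contact.
- Central nervous system and non-depressive psychiatric events after discharge: no dedicated measure. The PGIC may show general worsening. Otherwise capture rests on the participant or someone else telling staff.

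These figures count exposures and forms. The documents give no event rate and no capture rate, so the number of events missed or delayed cannot be calculated.

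**The case against.** The strongest reply is that the risk is low and the plan already matches its monitoring to it. Section 3 gives offset within a few minutes, and Section 10 regards the dose and duration as very safe. An hour of observation and a physician's discharge decision cover that window. Neither domain has a continuous monitor comparable to ECG or oximetry, so clinical assessment in the CRU is a reasonable method there. Section 4 excludes a history of bipolar disorder, schizophrenia or schizoaffective disorder, substance abuse or dependence (unless in remission for at least 1 year; nicotine excepted), and active psychotic symptoms. It also lets the principal investigator exclude any medical condition that raises the risk. All of this stands, and it limits the size of the point. It does not supply a question after discharge, and the plan itself allows 14 days for effects to wear off fully.

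A reader might infer three stronger things that the documents do not support:
- *That nobody monitors harm after discharge.* Section 8 commits the team to ongoing monitoring. What is missing is an active, scheduled enquiry.
- *That worsening depression goes unrecorded.* The PHQ-9 scores would contain it. What is missing is review and handling as an adverse event.
- *That nitrous oxide is likely to harm mood.* Section 2 reports improvement in depression, and nothing in the documents points the other way.

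Some material cannot be seen. The consent form and institutional guidelines are not in this copy and may tell participants how to report problems. The forms are not reproduced, so an item may prompt for adverse events. Section 6 (Blinding) places outcome assessment in CRU rooms, so one-week completion in person is possible. These limit certainty but do not describe an enquiry.

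**Conclusion.** The point holds as a minor one, with medium confidence. As described, capture of central nervous system and psychiatric events after the 100 minutes in the CRU depends on staff happening to learn of them. The gap is widest after session 2, where about 15 to 20 participants will have just received nitrous oxide and no later clinician contact is described. For depressive symptoms the gap is in review and action; for the other events it is in detection.

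This rests on three assumptions: the two orders stay balanced among completers, the forms carry no adverse-event item, and no document outside this copy schedules an enquiry. If either of the last two is wrong, the point shrinks to the PHQ-9 review step.

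**What to change.** In Section 7:
1. Add one open adverse-event question to the 1-day and 1-week forms for both sessions and to the forms completed before session 2. Word it to cover central nervous system and psychiatric events. It would also pick up nausea and vomiting after discharge, which Section 10 expects may occur and the four domains do not list.
2. List the PHQ-9 as a safety measure as well as an efficacy form.
3. Have REDCap alert the psychiatry sub-investigator when the PHQ-9 worsens from that session's baseline by an amount fixed in advance, or when an answer indicates self-harm, if the version used asks about it. The alert should carry no treatment allocation, so the blind is kept. State how soon it must be reviewed.

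The cost is one question on existing forms, one alert on a form already collected, and some time from a psychiatrist already on the team. The downside is some false alerts and a few more minor adverse events to report.
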